mCRC	Metastatic colorectal cancer
MedDRA	Medical Dictionary for Regulatory Activities
MEK	Mitogen-activated protein kinase
MRI	Magnetic Resonance Imaging
MTD	Maximum Tolerated Dose
NRAS	Neuroblastoma RAS viral oncogene homolog
OAT	Organic anion transporter
ORR	Objective Response Rate
OS	Overall Survival
PD	Pharmacodynamic / Progressive Disease
PDI	Planned dose intensity
PFS	Progression-Free Survival
P-gp	Permeability glycoprotein
PI3K	Phosphatidylinositol 3' Kinase
PIK3CA	Phosphatidylinositol 3' Kinase Catalytic Alphapolypeptide
PK	Pharmacokinetic
PR	Partial Response
PT	Prothrombin time
PTEN	Phosphatase and Tensin Homolog gene
QD	Quaque Die/ once daily
QOD	Every other day
QTcB	QT interval adjusted according to Bazett
QTcF	QT interval adjusted according to Fredericia
RAF	V-raf murine sarcoma viral oncogene
RAP	Report and Analysis Plan
RBC	Red Blood Cell
RDI	Relative dose intensity
RECIST	Response Evaluation Criteria In Solid Tumors
RP2D	Recommended Phase II Dose
RT-PCR	Reverse-transcriptase polymerase chain reaction
SAE	Serious Adverse Event
SD	Stable Disease
SOD	Sum of Diameters
t1/2	Terminal elimination half-life
t _{max}	Time to reach maximum plasma concentration

Version 2.2

TSH	Thyroid-stimulating hormone
TTR	Time To (overall) Response
VAP	Validation and Analysis Planning
WBC	White Blood Cell
WHO	World Health Organization

1 Introduction

This document provides the detailed statistical methodology for the analysis of data for initial interim Clinical Study Report (CSR) of the study CMEK162X2110 (C4221005) as well as the final CSR.

An initial interim CSR will be prepared based on all Phase Ib/Phase II patient data from the dual study drug combination. The cut-off for reporting will be either LPFV + 18 months or when 80% of the patients can be assessed for progression free survival (PFS), whichever occurs first. Additional data for patients continuing to receive the MEK162 and LGX818 dual combination beyond the cutoff point for the initial reporting, as allowed by the protocol, and the Phase Ib/II data from the LGX818 and MEK162 and LEE011 triple combination will be summarized in a final CSR once all patients have discontinued the study. Although this SAP provides comprehensive detail on analyses performed throughout the lifetime of the study, only analyses included in the appendices for the final CSR (Section 4: Final Analysis Appendices) will be performed for the final analysis. For the presentation of results in the final analysis, LGX818, MEK162, and LEE011 will be referred to by their respective generic names: encorafenib, binimetinib, and ribociclib.

In this document, the dual and triple combination refers to the combination of LGX818 and MEK162, and LGX818 and MEK162 and LEE011, respectively, when not specified.

The purpose of the CSRs is to report the estimated maximum tolerated dose (MTD) and/or recommended phase II dose (RP2D), characterize the dose limiting toxicities (DLT), safety profile and efficacy of LGX818/MEK162 and LGX818/MEK162/LEE011 combinations in patients with solid tumors harboring a BRAF V600 mutation.

In addition, the CSR also report the assessment of clinical efficacy and safety of the LGX818 and MEK162 combination in patients with BRAF V600 mutant metastatic colorectal cancer (mCRC), patient with BRAF V600 mutant metastatic melanoma, who have progressed after prior selective BRAF inhibitor and patient with BRAF V600 mutant metastatic melanoma, who are naïve to prior selective BRAF inhibitor treatment.

[figure not shown]
An interim analysis is planned for the phase II part of patients with BRAF V600 mutant mCRC, when 50% of the total sample size (14 patients) have completed four cycles of treatment, to allow stopping early for futility when there is no treatment effect.

[figure not shown]
Note that obvious corrections will be made at the time of analysis to address minor formatting or spelling mistakes present in the SAP without the need to amend this document.

1.1 Study design

This is a multi-center, open-label, dose finding, Phase Ib dose escalation study to estimate the MTD(s) and/or RP2D(s) for the combination of LGX818 and MEK162 and triple combination of LGX818 and MEK162 and LEE011, followed each independently by a Phase II part to assess the clinical efficacy and to further assess the safety of the combinations in selected patient populations.

Oral LGX818 and MEK162 will be administered once daily and twice daily, respectively, on a continuous schedule. Oral LGX818 and MEK162 and LEE011 will be administered once daily on a continuous schedule (LGX818), twice daily on a continuous schedule (MEK162) and once daily three week on, one week off (LEE011), respectively. Patient will be treated until progression of disease, unacceptable toxicity develops, or withdrawal of infored consent, whichever occurs first. Continued treatment beyond progression of disease will be allowed under certain circumstances.

Dose escalation (Phase Ib)

The dose escalation part of the trial will be conducted in adult patients with BRAF V600dependent advance solid tumors. This part of the trial is expected to enroll at least 18 patients for the dual combination and at least 12 patients for the triple combination. For the purposes of the dose escalation decisions, each cohort will consist of 3 to 6 newly enrolled patients. The successive cohorts of patients will receive increasing doses of the combinations. The first cohort for the dual combination will be treated with the starting combination doses of 50 mg once daily (qd) for LGX818 and 45 mg twice daily (bid) for MEK162. The first cohort for the triple combination will be treated with the starting combination doses of 200 mg once daily (qd) for LGX818, 45 mg twice daily (bid) for MEK162 and 100 mg once daily (qd) for LEE011 (3 weeks on/1 week off regimen).

Once all patients in a dose cohort have completed 28 days (1 cycle) of treatment and an assessment of their dose limiting toxicity (DLT) status is performed, the adaptive Bayesian logistic regression model (BLRM) will be updated. At each decision time point, the adaptive BLRM provides the upper boundary for the combinations that meet the escalation with overdose control (EWOC) criteria. The clinical synthesis of the available toxicity information,

pharmacokinetic (PK), **CC** and efficacy, as well as the recommendations from the adaptive BLRM are used to determine the dose combination for the next cohort(s). The Sponsor and investigators will decide on next dose levels and dosing schedule(s) to be explored at the dose escalation teleconference.

Various dose levels will be explored until the MTD is determined and/or until a consensus between the Sponsor and Investigators is reached and it is considered that there is no benefit of further increasing the dose. At this time the RP2D, a dose less than or equal to the MTD, will be estimated based on a review of the totality of the available study data. At least 6 patients eligible for the dose determining analysis set (DDS) must be treated at the dose(s) declared to be the MTD/RP2D. More than one dose-combination may be identified as a MTD, and more than one RP2D may be established for further evaluation in the phase II part of the study. In the case that all dose combinations are considered to be too toxic by the adaptive BLRM after the first cohort, no MTD/RP2D can be defined.

Phase II

Following MTD/RP2D declaration, for the dual combination patients will be enrolled in three Phase II arms.

- Phase II Arm 1 will assess the disease control rate (DCR) of the dual combination in patients with BRAF V600 mutant mCRC.
- Phase II Arm 2 will assess the objective response rate (ORR) of the dual combination in patients with BRAF V600 mutant melanoma who have progressed after prior selective BRAF inhibitor treatment.
- Phase II Arm 3 will assess the ORR of the dual combination in metastatic BRAF mutant melanoma patients who are naïve to prior treatment with a selective BRAF inhibitor.

Following MTD/RP2D declaration, for the triple combination patients will be enrolled in an additional Phase II arm.

• Phase II Arm A will assess the objective response rate (ORR) of the triple combination in patients with locally advanced or metastatic BRAF V600 mutant melanoma who are naïve to previous treatment with a selective BRAF inhibitor.

Phase II arms will also assess the safety of the combinations.

If more than one dose combination or dosing schedule has been defined as MTD/RP2D, The Sponsor may decide to open the Phase II arms for more than one MTD/RP2D and/or start the Phase II arms with different dose combinations or schedules.

1.2 **Objectives and endpoints**

The study objectives and corresponding endpoints are shown in Table 1-1.

Table 1-1Objectives and related endpoints

Objective	Endpoint

Primary	
Phase Ib: To estimate the MTD(s) and/or RP2D(s) of oral LGX818 in combination with oral MEK162, and of oral LGX818 in combination with oral MEK162 and oral LEE011 in patients with BRAF V600- dependent advanced solid tumors	Phase lb: Incidence of Dose Limiting Toxicities
 Phase II: To assess clinical efficacy of the LGX818 and MEK162 dual combination and LGX818 and MEK162 and LEE011 triple combination in the respective Phase II populations: Arm 1: metastatic BRAF V600 mutant mCRC patients (dual combination) Arm 2: metastatic BRAF V600 mutant melanoma patients who have progressed after prior selective BRAFi treatment (dual combination) Arm 3/ Arm A: metastatic BRAF V600 mutant melanoma patients who are naïve to prior selective BRAFi treatment (dual and triple combination). 	Phase II arm 1: Disease control rate (DCR) as per RECIST v1.1 Phase II arms 2 and 3 / Phase II arm A: Objective Response Rate (ORR) as per RECIST v1.1
Secondary	
Phase lb + II: To characterize the safety and tolerability of LGX818 and MEK162 in combination, and LGX818 and MEK162 and LEE011 in combination	Phase lb + II Incidence and severity of AE
Phase lb To determine the single and multiple dose PK profile of the LGX818 and MEK162 combination, and of the LGX818 and MEK162 and LEE011 combination To assess preliminary clinical anti-tumor activity of the LGX818 and MEK162 combination, and of the LGX818 and MEK162 and LEE011 combination	Phase lb Time vs. plasma concentration, basic PK parameters of LGX818 and MEK162 and LEE011 and known active metabolite(s) ORR as per RECIST v1.1
Phase II To further assess clinical efficacy of the LGX818 and MEK162 dual combination and of the LGX818 and MEK162 and LEE011 triple combination in the Phase II populations	Phase II Progression free survival (PFS), time to response (TTR), duration of response (DOR) as per RECIST v1.1, and Overall Survival (OS)

To characterize baseline molecular status of

molecules relevant to RAF/MEK/ERK and

EFGR/ PI3K/AKT signaling in tumor tissue

Baseline molecular status (mutation/amplification/expression) in tumor tissue of potential predictive markers of tumor response or resistance (BRAF, HRAS, KRAS, NRAS, PTEN, cKIT, PIK3CA, MAP2K1, MAP2K2, ARAF, c-MET, RAF1, EGFR)

1.3 Data Analysis

Data will be analyzed by the Sponsor and/or designated CRO according to the data analysis section 10 of the clinical study protocol [CMEK162X2110] and will be available in CSR Appendix 16.1. Impoltant infolmation will be given in the following sections and details are provided as applicable in CSR Appendix 16.1.9.

The Bayesian modelling of the analysis will be nm using R version 2-13.2 and WinBUGS Version 1.4.3 in the MODESIM (production) and GPS II environments. Other statistical analysis will be perfo1med using SAS® version 9.2 or higher.

The following rnles will be followed for reporting results unless stated othelwise:

Phase lb dose escalation data: Coholts of patients treated with the same dose combination and regimen during the dose escalation part will be pooled into a common treatment group. All summaries, listings, figures and analyses will be display/perfolmed by treatment group unless othelwise specified.

Phase II data: Data will be summarized and listed by arm (See Section 2.1.1).

Phase lb/II combined data: Data will be summarized and listed by ann and treatment group (See Section 2.1.1).

Screen failure patients are those who signed the infolmed consent, but never staited the study treatment for any reason. For these patients, the only infolmation collected on the eCRF will be the screening log and the demography pages. These will not be included in any analysis, but will be reported in the CSR as sepai-ate listings.

1.4 Analysis not according to the protocol

The protocol lists the primaiy vai iable of Phase 2 data as the estimation of trne DCR and ORR by ann using a Bayesian design. Instead a frequentist approach will be used for the analysis of DCR and ORR of the Phase 2 data presenting the observed value and exact confidence interval.

1.5 CSR related reporting events

The following points will guide the production of all or subset of the planned analyses:

- The initial interim CSR (refened to as the initial CSR in protocol) includes all outputs described for the dual combination, with the data cut-off of August 31, 2015. This SAP describes the analysis for the initial interim CSR.
- The final CSR includes all outputs described for the triple combination and listing for the dual combination, with the data cut-off on or after all patients have completed or discontinued from the study.
- CCI

2 Definitions and general methodology

2.1 General definitions

2.1.1 Study drug and study treatment

2.1.1.1 Naming conventions

Study drug refers to any investigational drug(s) being used for an unapproved indication. Study treatment refers to any combination of study drugs(s).

Study treatment:

- Dual combination = LGX818 + MEK162
- Triple combination = LGX818 + MEK162 + LEE011

Other naming conventions

"Study parts" or "Study phase": refers to the sequential parts of the study:

- Phase Ib (dose escalation)
- Phase II

Phase Ib for the dual and triple combination

- "Cohort" or "Dose Cohort": group of typically 3 to 6 patients enrolled sequentially at once during the dose escalation and intended to receive the same dose of study treatment.
- "Treatment group": group of patients intended to receive the same study treatment, for instance same dose level of study treatment. A treatment group can include several cohorts of patients who have received the same dose level but were recruited at different point in the study.

For example, for dual combination subjects:

Treat. A = LGX818 50 mg qd and MEK162 45 mg bid

Treat. B = LGX818 100 mg qd and MEK162 45 mg bid

•••

All dual combo patients = All dual combination patients

For example, for triple combination subjects:

Treat. A = MEK162 45 mg BID and LGX818 200 mg QD and LEE011 100 mg QD Treat. B = MEK162 45 mg BID and LGX818 200 mg QD and LEE011 200 mg QD ...

All triplet combo patients = All triple combination patients

Phase II for the dual and triple combination

• "Phase II arm": refer to separate groups of patients to be displayed separately according to study design even if receiving the same treatment. For example, for dual combination subjects: Phase II arm 1, refer to patients with BRAF V600 mCRC

Phase II arm 2, refer to patients with BRAF V600 mutant melanoma who have progressed after prior selective BRAF inhibitor treatment

Phase II arm 3, refer to patients with BRAF V600 mutant melanoma who are naïve to prior selective BRAF inhibitor treatment

All dual combo patients = All dual combination patients

For example, for triple combination subjects:

BRAF mutant melanoma no prior BRAF inhibitor

All triple combo patients = All triple combination patients

Phase 1b/II combined for the dual combination

• The Phase Ib patients in the LGX818 400/450/600 mg treatment groups whose disease matches one of the Phase II arms will be combined with Phase II data in the by arm and treatment group.

Arm 1, refers to BRAF V600 mutant mCRC

Treat. A, refers to LGX818 400/450 mg qd and MEK162 45 mg bid

Treat. B, refers to LGX818 600 mg qd and MEK162 45 mg bid

Arm 2, refers to BRAF V600 mutant melanoma who have progressed after prior selective BRAF inhibitor treatment

Treat. A, refers to LGX818 400/450 mg qd and MEK162 45 mg bid

Treat. B, refers to LGX818 600 mg qd and MEK162 45 mg bid

Arm 3, refers to BRAF V600 mutant melanoma who are naïve to prior selective BRAF inhibitor treatment

Treat. A, refers to LGX818 400/450 mg qd and MEK162 45 mg bid Treat. B, refers to LGX818 600 mg qd and MEK162 45 mg bid

Phase 1b/II combined for the triple combination

• The Phase Ib patients in the LEE011 100/200/400/600 mg treatment groups whose disease matches the Phase II arm will be combined with Phase II data in the by treatment group/arm analyses.

Arm 1, refers to BRAF mutant melanoma no prior BRAF inhibitor

Treat. A, refers to LGX818 200 mg QD and MEK162 45 mg BID and LEE011 100 mg QD $\,$

Treat. B, refers to LGX818 200 mg QD and MEK162 45 mg BID and LEE011 200 mg QD

Treat. C, refers to LGX818 200 mg QD and MEK162 45 mg BID and LEE011 400 mg QD

Treat. D, refers to LGX818 200 mg QD and MEK162 45 mg BID and LEE011 600 mg QD

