Table 14.2.4.1d	Analysis of time to response as per local assessment using Kaplan-Meier method by arm	Full Analysis Set	Phase II, Triple Combination, Confirmed Responders
Table 14.2.5.1b	Analysis of duration of response as per local assessment using Kaplan- Meier method by arm	Full Analysis Set	Phase II, Dual Combination, Confirmed Responders
Table 14.2.5.1d	Analysis of duration of response as per local assessment using Kaplan- Meier method arm	Full Analysis Set	Phase II, Triple Combination, Confirmed Responders
Table 14.3.1.1.1d	Dose limiting toxicities occurring during the first 28 days by primary system organ class, preferred term and treatment group	Dose Determining Set	Phase Ib, Triple Combination
Table 14.3.1.2.1d	Treatment-emergent adverse events (all causality) by preferred term, maximum grade (grades 1-4) and treatment group/arm	Safety Set	Phase Ib/II, Triple Combination
Table 14.3.1.2.2a	Treatment-emergent adverse events (all causality) by preferred term, maximum grade (overall and grade 3/4) and treatment group	Safety Set	Phase Ib, Dual Combination
Table 14.3.1.2.2b	Treatment-emergent adverse events (all causality) by preferred term, maximum grade (overall and grade 3/4) and arm	Safety Set	Phase II, Dual Combination
Table 14.3.1.2.2d	Treatment-emergent adverse events (all causality by preferred term, maximum grade (overall and grade 3/4), and treatment group/arm	Safety Set	Phase Ib/II, Triple Combination
Table 14.3.1.2.3d	Serious adverse events (all causality) by preferred term, maximum grade (overall and grade 3/4), and treatment group/arm	Safety Set	Phase Ib/II, Triple Combination
Table 14.3.1.2.4a	Treatment-emergent adverse events leading to permanent study drug discontinuation (all causality) by preferred term, maximum grade (grades 1-4) and treatment group	Safety Set	Phase Ib, Dual Combination
Table 14.3.1.2.4b	Treatment-emergent adverse events leading to permanent study drug discontinuation (all causality) by preferred term, maximum grade	Safety Set	Phase II, Dual Combination

Pfizer Inc.

	(grades 1-4) and arm		
Table 14.3.1.2.4d	Treatment-emergent adverse events leading to permanent study drug discontinuation (all causality)by class, preferred term, maximum grade (grades 1-4) and treatment group/arm	Safety Set	Phase Ib/II, Triple Combination

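### The triple-combination Phase Ib/II tables have two possible denominators, because a disease-match pooling rule conflicts with the unrestricted Safety Set

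*SAP*

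**What the plan says.** Section 1.1 opens Phase Ib to a broad population: "The dose escalation part of the trial will be conducted in adult patients with BRAF V600dependent advance solid tumors". It plans "at least 12 patients for the triple combination" in that part. Phase II Arm A is narrower, namely BRAF V600 mutant melanoma naive to a selective BRAF inhibitor.

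Section 1.3 refers the reader to Section 2.1.1 for how combined Phase Ib/II data are presented. There, Section 2.1.1.1 states that Phase Ib patients at the four LEE011 dose levels "whose disease matches the Phase II arm will be combined with Phase II data in the by treatment group/arm analyses". One population follows, "Arm 1, refers to BRAF mutant melanoma no prior BRAF inhibitor", split into Treat. A to D by LEE011 dose. An all-triple total is defined under the separate Phase Ib and Phase II headings, but not under the combined heading.

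Section 4.1.1 lists the triple safety tables with titles ending in treatment group/arm and the subset *Phase Ib/II, Triple Combination*. Table 14.3.1.2.3d is typical: "Serious adverse events (all causality) by preferred term, maximum grade (overall and grade 3/4), and treatment group/arm". The Introduction closes the list, since "only analyses included in the appendices for the final CSR (Section 4: Final Analysis Appendices) will be performed for the final analysis".

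Other sections carry no disease restriction:
- Section 2.2 admits to the Safety Set every patient dosed with any of the three drugs who has a valid post-baseline safety assessment.
- Section 3.6 uses that set for all Section 14 safety data except DLTs.
- Section 2.1.1.2 places each patient in exactly one treatment group/arm.
- Section 3.5 requires the Phase Ib ORR, with an exact interval, by treatment group.

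**The concern.** A dosed Phase Ib patient with colorectal cancer, another BRAF V600 tumour or BRAF-inhibitor-pretreated melanoma has no column in the combined set as Section 2.1.1.1 defines it. The outputs that would report that patient's safety all carry the combined label. A programmer working from Section 2.1.1.1 would leave the patient out, and one working from Sections 2.2 and 3.6 would keep the patient in.

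Safety of the triple combination across Phase Ib and II is a secondary objective (Table 1-1). Tumour type and prior BRAF inhibitor are not grounds for leaving a treated patient out of a safety summary. On the literal reading, event rates by dose would rest on a selected subset. A DLT could then be counted in Table 14.3.1.1.1d while the same event is missing from the adverse event tables for that dose group. The Phase Ib ORR objective is exposed in the same way, because Table 14.2.1.1d is the only triple response table.

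**Working it through.** The plan gives no figure to reproduce here. The check is a count of outputs, a comparison of sections and an illustration of scale.

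**1. Triple tables in the 14.3 series (Section 4.1.1)**

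| Block | Tables | Set and subset |
|---|---|---|
| 14.3.1.1.1d (DLT) | 1 | Dose Determining Set, Phase Ib |
| 14.3.1.2.1d to .7d | 7 | Safety Set, Phase Ib/II |
| 14.3.1.3.1d to .3d | 3 | Safety Set, Phase Ib/II |
| 14.3.2.2.1d, .2d | 2 | Safety Set, Phase Ib/II |
| 14.3.4.1.1d to .7d | 7 | Safety Set, Phase Ib/II |
| 14.3.5.2d | 1 | Safety Set, Phase Ib/II |
| 14.3.6.2.1d to .3d | 3 | Safety Set, Phase Ib/II |
| 14.3.7.1d | 1 | Safety Set, Phase Ib/II |
| 14.3.8.1d | 1 | Safety Set, Phase Ib/II |

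Safety Set tables: 7 + 3 + 2 + 7 + 1 + 3 + 1 + 1 = 25. With the DLT table the total is 26. Phase Ib-only triple tables of adverse events, SAEs, deaths or laboratory data: 0. The dual combination, by contrast, has Phase Ib versions (suffix a) of its main adverse event and death tables.

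**2. Does the match rule reach these tables?** Section 1.3 sends combined data to Section 2.1.1. The rule there speaks of treatment group/arm analyses, and the table titles use the same phrase. For the dual combination, Table 14.4.1.4 has separate Phase Ib (a), Phase II (b) and Phase Ib/II (c) versions, so there the combined label marks a distinct pool. On this route the rule applies.

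**3. Where it collides.** The Safety Set is not restricted by disease (Section 2.2) and serves all Section 14 safety data except DLTs (Section 3.6). The one-group rule (Section 2.1.1.2) cannot be met for a patient to whom the combined set gives no group. Phase Ib ORR by treatment group (Section 3.5) has no triple table other than 14.2.1.1d, which carries the combined label.

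**4. Scale, under assumptions.** The plan gives no match rate. Take the planned minimum of 12 triple Phase Ib patients and assume that 25%, 50% or 75% do not match. Then 12 × 0.25 = 3, 12 × 0.50 = 6 and 12 × 0.75 = 9 drop out on the literal reading. The chance that an event of true rate p is seen at least once among the n Phase Ib patients kept is 1 − (1 − p)^n:

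| Kept (n) | Dropped | p = 10% | p = 15% |
|---|---|---|---|
| 12 | 0 | 71.8% | 85.8% |
| 9 | 3 | 61.3% | 76.8% |
| 6 | 6 | 46.9% | 62.3% |
| 3 | 9 | 27.1% | 38.6% |

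The match shares and event rates are assumptions, and the figures count Phase Ib patients only.

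**The case against.** The sentence in Section 2.1.1.1 is a pooling rule. It says which Phase Ib patients join the Phase II data and nowhere says that the others leave the safety summaries. Several sections point to all treated patients being shown:
- Sections 2.2, 3.6 and 2.1.1.2, as set out above.
- Section 1.3, which reports Phase Ib data by treatment group unless otherwise specified.
- Section 3, which promises summaries by treatment group and overall where appropriate.

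The label itself may be loose. Section 3.5.3.1 says that PFS for the figure is also calculated for the Phase Ib treatment arms, and Figure 14.2.1.2d carries the combined label. That suggests Phase Ib groups displayed beside the Phase II arm. Table 14.1.1.1.1d, which accounts for the analysis sets, has the same label, and restricting it by disease would be odd.

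This stands to the extent that exclusion is not established. It does not remove the problem. The combined heading names one population and no total, Section 1.3 directs combined data to that section, and no listed Phase Ib triple table of adverse events shows where the other patients go.

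The illustration of scale is open to a fair objection too. The tables also contain Arm A, so the percentages overstate the chance that an event goes untabulated altogether.

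**Conclusion.** The plan contains an unresolved contradiction that gives two possible denominators for the 25 triple Safety Set tables in the 14.3 series, the triple disposition and exposure tables, and Table 14.2.1.1d. Which one is used would depend on which section the programmer follows.

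A reader might infer that treated Phase Ib patients are certain to disappear from every triple safety output. The documents do not support that. DLT Table 14.3.1.1.1d keeps any such patient who is in the Dose Determining Set. Listing 16.2.7.1 shows adverse events and Listing 16.2.6.1 shows responses on the FAS without a subset. The sections cited above also favour full inclusion.

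The number of patients affected cannot be read from the plan. It lies between zero and all of the triple Phase Ib patients, of whom at least 12 are planned. The figures of 3, 6 and 9 rest wholly on assumed match rates.

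**What to change.** - In Section 2.1.1.1, limit the disease-match rule for the triple combination to efficacy pooling by arm. Also correct the label there: the population called Arm 1 is Arm A in Section 1.1.
- State that the triple disposition, exposure and safety tables include every FAS or Safety Set patient, as each table specifies. The columns would be Phase Ib by dose group regardless of tumour type or prior BRAF inhibitor, Phase II Arm A, and an all-triple total.
- In Table 14.2.1.1d, report the Phase Ib ORR by dose group for all Phase Ib triple patients.
- Reconcile Figure 14.2.1.2d with Section 3.5.3.1 by stating which Phase Ib patients its curves contain.

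The cost is SAP wording and column definitions in tables already listed. No new data are needed.
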